## 2.4 Treatments and Assignment to Treatments

Enrollment will start in the Arm A dose evaluation cohorts in a sequential fashion. After the RCD is determined for Arm A, enrollment will start for the dose evaluation of Arm B and for the Arm A Expansion Cohort, whereby no randomizations will be performed. Any new subject will be assigned to the Arm B dose evaluation cohort, unless no slot is available, in which case the subject will be assigned to the Arm A Expansion Cohort. After the dose evaluation and safety review for Arm B is complete, enrollment into the Arm B Expansion Cohort Group will be prioritized over Arm A.

Figure 1: Enrollment Schema for Arms A and B

\* After the dose evaluation and safety review for Arm B is complete, enrollment into the Arm B Expansion Cohort will be prioritized over Arm A.

## 2.5 Determination of Sample Size

The dose evaluation phase will utilize a standard 3 + 3 design for Arms A and B, which will result in the enrollment of 6 to 18 subjects.

In the expansion phase, 20 subjects per arm are thought to provide sufficient data to adequately identify essential safety and preliminary efficacy signals. Therefore, up to 14 additional subjects will be added to the 6 subjects treated at the RCD in each arm (A and B).

The sample size  $n=20$  for the expansion phase is deemed to provide sufficient precision for the estimation of incidence of adverse events as estimated by the Clopper Pearson confidence intervals (CI) for incidence of adverse events.

Overall, approximately 56 subjects will be enrolled in up to 8 sites in the US. The enrollment period will take approximately 24 months.

### 3.0 GENERAL ANALYSIS CONVENTIONS

#### 3.1 General Conventions

Data collected in this study will be documented using summary tables and subject data listings. Continuous endpoints will be summarized using descriptive statistics, e.g. number of subjects, mean, median, standard deviation, minimum and maximum values. The mean and median will be reported to 1 decimal place more than the level of precision of the data being reported and the SD will be reported to 2 decimal places more than the level of precision of the data being reported, unless otherwise noted. Categorical endpoints will be presented in frequency tables with number and percentage of observations for each level.

All efficacy analyses will be presented separately for Arm A and Arm B. Tumor Response will be summarized and analyzed descriptively. A 95% Confidence Interval based on the binomial distribution will be constructed for the estimated PFS rate and ORR at 8 and 24 weeks and DCR.

The number and percentage of subjects who died or had a confirmed progression, who survived without a confirmed progression, and who were lost to follow up (unknown survival and/or progression status) will be summarized.

PFS rate at 8 and 24 weeks and the corresponding 95% CIs will be calculated based on Kaplan-Meier product limit estimates and will be displayed along with the corresponding number of subjects at risk. (Note – this may include OS as well)

PFS and OS will be summarized using the 25th percentile, Median, and 75th percentile as well as the minimum and maximum survival time, calculated by Kaplan-Meier method, and will be displayed graphically.

The ORR, DCR and DOR will be summarized descriptively and a 95% Confidence Interval based on binomial distribution will be presented.

#### 3.2 Trial Periods

The overall length of study per subject is up to 15 months; comprising of 12 months for treatment and three months for on study follow-up. The screening period is up to one month prior to first drug administration.

Study drug will be administered over 12 cycles with a cycle length of 28 days. The study drugs used in this study will be administered per cycle as shown in Appendix B.

The overall length of the study is 39 months. However the length of the survival post study follow-up is up to five years from initiation of treatment.

### 3.3 Visit Windows

The allowed visit windows are defined as shown in Table 1. Visits will be analyzed per the eCRF collection.

Table 1: Visit Windows

Visit Name	Allowed window (Cycle Day $\pm$ Window)
Screening	Day -28 to -1
Weeks 2, 3, 5, 6, 7, 9, 11, 13, 14	+/- 2 day
Weeks 17, 21, 25, 27	+/- 3 day
Week 28	+/- 2 day
Weeks 29, 33, 37, 39, 41, 45	+/- 3 day
Week 46	+/- 2 day
On study Follow-up	28 (+/-4) days post last dose 42 (+/-4) days post last dose 91 (+/-7) days post last dose
Post Study Follow-up	Every 6 months until 5 years

Note: Visit days are defined from baseline (Cycle 1, Day 1 visit).

Vaccinations may have to be delayed to allow for recovery of AEs prior to continuation of vaccine treatment. After the delayed vaccination all subsequent vaccinations must be continued within the schedule relative to the first vaccination presented in the flow chart.

### 3.4 Baseline

Unless specified otherwise, baseline measurements will be the most recent value prior to receiving the first dose of study medication.

## 4.0 ANALYSIS POPULATIONS

### 4.1 Intent-to-Treat Population

The Intent-To-Treat (ITT) Population is defined as all subjects who receive at least one dose of any of the study drugs. This population will be used for safety and efficacy analyses.

### 4.2 Per-Protocol Population (Clinical Efficacy)

The Per-Protocol (PP) Population (Clinical Efficacy) is defined as all subjects who received at least 75% of the scheduled doses of durvalumab and tremelimumab and at least 4 of the 5 BI 1361849 vaccinations over the first 2 cycles, as well as, respective disease assessments (irRECIST or RECIST, clinical progression or death), without major protocol violations. Efficacy analyses will also be presented for PP population.

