## 2.2 Durvalumab and Tremelimumab Dose

Currently, fixed dosing is recommended for durvalumab and tremelimumab with the dose and schedule of 1500 mg durvalumab Q4W and 75 mg tremelimumab Q4W for subjects > 30 kg.

A population PK model was developed for durvalumab using monotherapy data from a Phase 1 study (*Study 1108; N=292; doses= 0.1 to 10 mg/kg Q2W or 15 mg/kg Q3W; solid tumors*). Population PK analysis indicated only minor impact of body weight on PK of durvalumab (coefficient of  $\leq 0.5$ ). The impact of body weight-based (10 mg/kg Q2W) and fixed dosing (750 mg Q2W) of durvalumab was evaluated by comparing predicted steady state PK concentrations (5th, median and 95th percentiles) using the population PK model. A fixed dose of 750 mg was selected to approximate 10 mg/kg (based on median body weight of approximately 75 kg). A total of 1000 patients were simulated using body weight distribution of 40–120 kg. Simulation results demonstrate that body weight-based and fixed dosing regimens yield similar median steady state PK concentrations with slightly less overall between-subject variability with fixed dosing regimen.

Similarly, a population PK model was developed for tremelimumab using data from Phase 1 through Phase 3 (*N=654; doses= 0.01 to 15 mg/kg Q4W or Q90D; metastatic melanoma*). Population PK model indicated minor impact of body weight on PK of tremelimumab (coefficient of  $\leq 0.5$ ). The weight-based (1 mg/kg Q4W) and fixed dosing (75 mg/kg Q4W; based on median body weight of approximately 75 kg) regimens were compared using predicted PK concentrations (5th, median and 95th percentiles) using population PK model in a simulated population of 1000 patients with body weight distribution of 40 to 120 kg. Similar to durvalumab, simulations indicated that both body weight-based and fixed dosing regimens of tremelimumab yield similar median steady state PK concentrations with slightly less between-subject variability with fixed dosing regimen.

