### 3.1.7 Treatment Arms and Treatment Schema

Study drug will be administered over 12 cycles with a cycle length of 28 days. The study drugs used in this study will be administered per cycle as shown below:

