### **3.1.11 Subject Evaluability and Subject Replacements**

In the *dose evaluation phase*, subjects are fully evaluable for DLT if they fulfill the criteria for the Per-Protocol Population for DLT Assessment (as defined in Section 4.1.2).

Subjects who are not fully evaluable for DLT per Section 4.1.2 will be replaced.

Subjects are fully evaluable for secondary endpoints of PFS rate and ORR, if they fulfill the criteria for the Per-Protocol Population for Clinical Efficacy (as defined in Section 4.2.2).

Subjects who are not fully evaluable for PFS rate and ORR may be replaced.

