### **4.2.2 Subject Evaluation and Statistics**

The Intent-To-Treat (ITT) Population is defined as all subjects who receive at least one dose of any of the study drugs.

The **Per-Protocol (PP) Population for Clinical Efficacy** is defined as all subjects who received at least 75% of the scheduled doses of durvalumab and tremelimumab and at least 4 of the 5 BI 1361849 vaccinations over the first 2 cycles, as well as, respective disease assessments, without major protocol violations.

All efficacy analyses will be based on both ITT and PP populations for each cohort.

Tumor Response will be summarized and analyzed descriptively for each arm and analysis population. A 95% Confidence Interval based on binomial distribution will be constructed for the estimated PFS rate and ORR at 8 and 24 weeks and DCR.

The number and percentage of subjects who died or had a confirmed progression, who survived without a confirmed progression, and who were lost to follow up (unknown survival and/or progression status) will be summarized.

PFS rate at 8 and 24 weeks and the corresponding 95% CIs will be calculated based on Kaplan-Meier product limit estimates and will be displayed along with the corresponding number of subjects at risk.

---

CONFIDENTIAL

PFS and OS will be summarized using the 25th percentile, Median, and 75th percentile as well as the minimum and maximum survival time, calculated by Kaplan-Meier method, and will be displayed graphically.

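### The per-protocol efficacy population drops subjects who die or stop for progression in Cycle 1, which inflates PP response, PFS and OS rates; ITT is not affected

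*SAP*

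**What the plan says.** SAP 4.2 and Protocol 4.2.2 set the same two exposure thresholds for the PP efficacy population. The antibody threshold is three quarters of the doses due. The vaccine threshold is "at least 4 of the 5 BI 1361849 vaccinations over the first 2 cycles". The SAP alone adds what counts as a disease assessment: "respective disease assessments (irRECIST or RECIST, clinical progression or death), without major protocol violations". Neither document relaxes the thresholds for a subject whose treatment ended because of death or progression.

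Protocol 3.1.11 ties evaluability for the efficacy endpoints to this population and adds: "Subjects who are not fully evaluable for PFS rate and ORR may be replaced". SAP 11.1 repeats the permission.

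On use, Protocol 4.2.2 states: "All efficacy analyses will be based on both ITT and PP populations for each cohort". ITT is every subject with at least one dose of any study drug (SAP 4.1). Neither document names one of the two as the primary efficacy population.

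**The concern.** PFS and OS run from the first dose (Protocol 4.2.1.4 and 4.2.1.5), but PP membership is settled about four weeks later and only for subjects still on treatment. The PP rates are therefore conditional on getting through Cycle 1, which is guarantee-time bias. Dropouts are meant to count as non-responders (Protocol 4.2.1.1 and 4.2.1.2; SAP 7.2 and 7.3), but a Cycle 1 dropout has already left the PP denominator, so that rule cannot act on PP.

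Two comparisons within the documents suggest that this was not intended:
- The per-protocol population for DLT (Protocol 4.1.2, SAP 4.3) keeps every subject with a DLT in the evaluation period whatever the doses received. It applies the same thresholds only to subjects without a DLT. The efficacy definition takes over the thresholds without the parallel exemption.
- Both durvalumab studies summarised in Protocol 1.2.1 counted subjects who discontinued for progression or death without a follow-up scan as evaluable for response. A PP ORR that drops such subjects is not like for like with the 26.7% and 27% quoted there for NSCLC.

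Replacement adds to the problem. If early failures may be replaced, replacement depends on outcome, and the new subjects pass through the same filter.

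**Working it through.** **Step 1: when the thresholds can first be met.** The antibodies are given every four weeks (Protocol 2.2: "1500 mg durvalumab Q4W and 75 mg tremelimumab Q4W") in 28-day cycles (Protocol 3.1.7: "Study drug will be administered over 12 cycles with a cycle length of 28 days"). The flowchart in Protocol 3.2 then gives, for Cycles 1 and 2:
- Antibody doses on Days 1 and 29: 0.75 × 2 = 1.5, so both are needed. If the two Arm B antibodies are pooled, 0.75 × 4 = 3, which still needs a Day 29 dose.
- Vaccinations on Days 1, 8, 15, 29 and 43: the earliest possible fourth is Day 29, or Day 43 if one of the first four was missed.

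The visit window is ±2 days (SAP 3.3), so the earliest date is Day 27. However the 75% is read, the vaccine count alone excludes anyone whose treatment ends in Cycle 1: at most 3 of 5 vaccinations have been given.

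**Step 2: the plan's own figures.** The only sample-size support is the Clopper-Pearson table for n = 20 in Protocol 3.1.6. All 19 intervals reproduce; 12/20 gives 36.1% to 80.9%.

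**Step 3: effect of the exclusion.** With r successes among 20 treated and k Cycle 1 failures dropped, the rate moves from r/20 to r/(20 − k). For r = 12 (progression-free at Week 8) and r = 5 (responders):

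| k | r = 12 | 95% CI | r = 5 |
|---|---|---|---|
| 0 (ITT) | 60.0% | 36.1% to 80.9% | 25.0% |
| 1 | 63.2% | 38.4% to 83.7% | 26.3% |
| 2 | 66.7% | 41.0% to 86.7% | 27.8% |
| 3 | 70.6% | 44.0% to 89.7% | 29.4% |
| 4 | 75.0% | 47.6% to 92.7% | 31.3% |

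Replacement refills the set without correcting it. With k = 3, a refilled PP of 20 is expected to hold 20 × 12/17 = 14.1 successes. The protocol's interval for 14/20 is 45.7% to 88.1%, narrower than that for 12/17 but around nearly the same raised value.

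**Step 4: a plausible range for k (assumption).** The documents give no early-failure rate. As an illustration, take exponential times with the medians quoted for the earlier vaccine trial (Protocol 1.2.3), which was in a maintenance setting: PFS 2.9 months and OS 14 months, at 30.4375 days per month. Then P(event within 28 days) = 1 − 2^(−28/median in days).
- Deaths only (426.1 days): 4.5%, or 0.9 of 20 subjects. The chance of at least one in 20 is 60%. Conditioning moves Week 8 survival from 91.3% to 95.5%, and an ORR of 27% to 28.3%.
- All PFS events (88.3 days): 19.7%, or 3.9 of 20. Week 8 PFS moves from 64.4% to 80.3%, Week 24 PFS from 26.7% to 33.3%, and an ORR of 27% to 33.6%.

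The second case is an upper bound under this model. The first scheduled scan is at Week 9 (Day 57), so most progression would not be recognised before Day 29.

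**Step 5: net direction.** The same dose rule also removes subjects who have not failed. Under Protocol 8.3.1 a toxicity hold can cost the Day 29 antibody dose. Dropping one early failure and one responder turns 5/20 = 25.0% into 4/18 = 22.2%, which is lower than ITT.

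**The case against.** The strongest reply is that ITT already answers the question. It is always reported, it holds every treated subject including any who were replaced, and SAP 5.0 requires removals from each population to be summarised. Efficacy is secondary and descriptive, no formal decision rule rests on PP, and conditioning on exposure is what a per-protocol set does. All of this stands and limits the weight of the point. It does not repair PP, which is reported for every efficacy analysis without being labelled as supportive.

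A reader might infer more than the documents support:
- **Every PP rate is biased upward.** Only this one exclusion has a fixed direction; Step 5 shows that the net can go the other way. DoR is computed in responders and is essentially unaffected.
- **Nobody who fails before Day 29 can qualify.** A dose may be given from Day 27, and dosing may continue past unconfirmed progression (Protocol 3.1.10.1). Both are corner cases; the affected group is deaths and progression that ends treatment.
- **The SAP contradicts itself.** The clause on death and clinical progression still does work: it admits subjects who meet the dose rule and then fail before the Week 9 scan.
- **The bias is worse in the arm with more toxicity stops.** Stopping for toxicity is censored for PFS, not counted as failure (Protocol 4.2.1.4, SAP 7.4).
- **The 10 of 63 not-evaluable subjects in the cited combination study measure early failure.** Protocol 1.2.1 does not say why they were not evaluable and counts progression separately.

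It can also be said that relaxing the thresholds for failures alone makes membership depend on outcome. The change below asks the same adherence of everyone while event-free and still excludes a subject who missed too many doses before failing. What remains is that an early failure has had fewer doses to miss, which is a further reason for ITT to lead.

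**Conclusion.** The point holds in limited form. The dose thresholds cannot be met before about Day 29, so PP excludes subjects who die or stop for progression in Cycle 1 and allows them to be replaced. That exclusion by itself raises PP ORR, DCR, PFS and OS rates: by 6.7, 10.6 or 15.0 percentage points on a 60% rate if 2, 3 or 4 of 20 subjects are affected, and by nothing if none are. The number affected is assumed, and all of these raised values lie inside the 36.1% to 80.9% interval for 12/20. ITT estimates do not carry this bias. The change is worth making because PP is reported throughout, neither population is named as primary, and the correction is small.

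**What to change.** - **SAP 4.2 and Protocol 4.2.2:** for subjects with PD, clinical progression or death within the first 2 cycles, apply the thresholds only to doses scheduled up to that date: at least 75% of antibody doses and no more than one missed vaccination. A subject adherent until a Day 20 death (1 antibody dose and 3 vaccinations due) then stays in PP as a failure. If all k early failures were adherent, each rate in Step 3 returns to r/20.
- **Protocol 3.1.11 and SAP 11.1, the PFS rate and ORR replacement sentence only:** do not replace subjects whose non-evaluability is due to progression or death, and state that any replaced subject stays in ITT. Leave the DLT replacement rule as it is.
- **Both documents:** name ITT as the primary efficacy population and PP as supportive.

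The cost is a short clause in each place and a small change to the population derivation. PP rates will be slightly less favourable, and PP will hold a few subjects with short exposure.

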### 4.3 Per-Protocol Population (DLT Assessments)

The Per-Protocol (PP) Population (DLT Assessments) is defined as follows:

- All subjects in the dose escalation who experience a DLT at any time during the DLT Evaluation Period (as defined in Section 3.1.9 of the protocol).
- All subjects with no DLT who receive at least 75% of the scheduled doses of durvalumab and tremelimumab and at least 4 of the 5 BI 1361849 vaccinations over the first 2 cycles as well as respective safety assessments without major protocol violations during the DLT Evaluation Period .

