### 3.1.9 DLT and MTD/RCD for the Combination Therapy

MTDs will not be determined in this study. Instead, RCDs will be determined in the context of the predefined dose levels used during the dose evaluation phase as per Section 3.1.7.1.

DLTs will be observed over a period of the first 2 cycles of the combination therapy, including the pre-dose assessment for Cycle 3, defined as the **DLT Evaluation Period**. The decisions for dose evaluations, de-escalations and RCD, as described in Section 3.1.7.1 will primarily be based on the number of subjects with DLTs occurring during the DLT Evaluation Period. DLTs occurring outside the DLT Evaluation Period will also be evaluated and may impact such decisions.

DLTs are defined as any adverse events that are possibly, probably, or definitely related to the administration of durvalumab, tremelimumab, or BI 1361849 components, and fulfill any of the following criteria:

1. Any Grade  $\geq 3$  colitis, pneumonitis, neurological event or uveitis.
2. Any Grade 2 pneumonitis, neurological event or uveitis, with the following exception:
  - Grade 2 pneumonitis, neurological event or uveitis that downgrade to Grade  $\leq 1$  within 3 days after onset, whereby maximal supportive care, including systemic corticosteroids, is permitted.
3. Any *other* Grade  $\geq 3$  toxicity, with the following exceptions:
  - Grade 3 irAEs that downgrade to Grade  $\leq 2$  within 3 days, or to Grade  $\leq 1$  or baseline within 14 days after onset, whereby maximal supportive care, including systemic corticosteroids, is permitted.
  - Grade 3 endocrinopathy that becomes asymptomatic when managed with or without systemic corticosteroid therapy and/or hormone replacement therapy.
  - Grade 3 inflammatory reaction attributed to a local antitumor response (e.g., inflammatory reaction at sites of metastatic disease, lymph nodes, etc.).
  - Grade 3 fatigue for  $\leq 7$  days.
  - Grade 3 infusion-related reaction (first occurrence and in the absence of steroid prophylaxis) that resolves within 6 hours with appropriate clinical management.
  - Liver transaminase elevation  $\leq 8$  times ULN that downgrades to Grade  $\leq 2$  ( $\leq 5$  times ULN) within 7 days after onset, whereby maximal supportive care, including systemic corticosteroids, is permitted.

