### 3.1.10 Subject Withdrawal from Treatment or from Study

A subject will be **withdrawn from study treatment** for any of the following reasons:

1. Withdrawal of consent for further treatment
2. Pregnancy or intent to become pregnant
3. DLT at any time (see Section 3.1.9)
4. Progressive disease requiring alternative systemic treatment
5. Significant protocol violation or noncompliance that, in the opinion of the Investigator or Sponsor, warrants withdrawal
6. Development of intercurrent, non-cancer-related illnesses or complications that prevent either continuation of therapy or regular follow-up
7. Best medical interest of the subject (at the discretion of the Investigator)

Discontinuation from receiving study treatment does not mean that the subject is withdrawn from the study. If applicable, subjects who are withdrawn from study treatment should undergo the planned On Study Follow-up procedures (see Study Flowchart, Section 3.2), followed by the Post Study follow-up period (see Section 3.1.16).

A subject will be **withdrawn from the study** for the following reasons:

1. Best medical interest of the subject at the discretion of the Investigator
2. Initiation of alternative anticancer therapy (marketed or investigational)
3. Withdrawal of consent for all follow-up
4. Lost to follow-up
5. Death

Section 7.2.6 provides additional details regarding documentation for early subject withdrawal from study treatment and early withdrawal from study.

See also Sections 8.3 and 8.4 for subject withdrawal from treatment due to necessary dosing interruptions or discontinuations.

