#### 4.1.2 Subject Evaluation and Statistics

The **Per-Protocol (PP) Population for DLT Assessment** includes:

- All subjects who experience a DLT at any time during the DLT Evaluation Period (as defined in Section 3.1.9)
- All subjects with no DLT who receive at least 75% of the scheduled doses of durvalumab and tremelimumab and at least 4 of the 5 BI 1361849 vaccinations as well as respective safety assessments without major protocol violations during the DLT Evaluation Period (as defined in Section 3.1.9)

Refer to Section 3.1.11 for subject replacement.

CONFIDENTIAL

The **Safety Population** is defined as all subjects who receive at least one dose of any of the study drugs.

In the dose evaluation phase, for the primary endpoint of determining DLTs and the RCD, the analysis of safety and tolerability will be based on the **PP Population for DLT Assessment**.

In both phases (evaluation and expansion), the overall analysis of safety and tolerability will be based on the **Safety Population**.

Appropriate summaries of AEs, SAEs, laboratory data and vital signs data will be presented for the Safety Population overall and by cohort. Adverse events will be coded using the MedDRA dictionary. Incidences of treatment-emergent adverse events (TEAE, those events that started after dosing or worsened in severity after dosing) will be presented overall and by maximum severity and relationship to study drugs.

For each continuous laboratory parameter, results will be categorized as low, normal, or high based on the laboratory normal ranges. Frequencies and percentages will be presented for the shifts in these categories (i.e., low to normal, low to high, high to low, etc.) from baseline to each post-treatment assessment time point. Additionally, for each continuous hematology and chemistry parameter, descriptive statistics will be presented for the changes from baseline to each post-treatment assessment time point. Descriptive statistics will be presented for the changes in vital signs from baseline to each post-treatment assessment time point.

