## 2.2 Study Endpoints

### Primary Endpoints

The primary endpoint of the combination therapy of durvalumab and tremelimumab are:

- Dose- Limiting Toxicities (DLTs). DLTs are defined as any adverse events that are possibly, probably, or definitely related to the administration of durvalumab, tremelimumab, or BI 1361849 components. This applies to Dose Evaluation subjects during the DLT Evaluation period.
- Safety and tolerability evaluated using CTCAE 4.03.
- Recommended Combination Dose (RCD) determined in Dose Evaluation Phase.

The safety endpoints for this study include:

[figure not shown]
- Treatment-emergent adverse events (TEAEs) and serious AEs (SAEs)
- Clinical laboratory tests (hematology and chemistry)
- Vital signs and weight measurements
- ECG
- ECOG performance status evaluation
- Any other medically indicated assessments, including subject interviews
- All safety analyses will be reported separately for Arm A and Arm B

The Clinical efficacy endpoints will be assessed by irRECIST and RECIST 1.1 and will include:

- Objective Response rate (ORR) at 8 and 24 weeks. ORR is defined as the percentage of subjects meeting criteria of Complete Response (CR) or Partial Response (PR) over a period of at least 4 weeks.
- Duration of Response (DoR). DoR is defined as the interval between the date of earliest determination of CR or PR to the date of earliest determination of PD, or to the date of death, if PD does not occur.
- Disease Control rate (DCR). DCR is defined as the percentage of subjects meeting criteria of Stable Disease (SD), PR, or CR over a period of at least 4 weeks.
- Progressive Free Survival (PFS) at 8 and 24 weeks. PFS is defined as the interval between the date of first dose to the date of earliest determination of Progressive Disease

(PD), or to the date of death, if PD does not occur. Week 8 corresponds to Cycle 3 Day 1 and Week 24 corresponds to Cycle 7 Day 1.

- Overall Survival (OS). OS is defined as the interval between the date of first dose until the date of death or the date of last follow-up.
- All efficacy analyses will be reported separately for Arm A and Arm B.

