## 5.0 SUBJECT DISPOSITION

Subject disposition will be summarized overall for all subjects who entered the study in a disposition table (i.e., signed the informed consent for the study). In addition, the number of subjects in each population (ITT and PP) and subjects that were removed from a population will be summarized. The number and proportion of subjects who complete the study, as well as those who discontinue the study will be summarized along with the reason for discontinuation.

Primary reason for treatment termination include the following criteria:

- Withdrawal of consent for further treatment
- Pregnancy or intent to become pregnant
- DLT at any time
- Progressive disease requiring alternative systemic treatment
- Significant protocol violation or noncompliance that, in the opinion of the Investigator or Sponsor, warrants withdrawal
- Development of intercurrent, non-cancer-related illnesses or complications that prevent either continuation of therapy or regular follow-up
- Best medical interest of the subject (at the discretion of the Investigator)

Primary reason for study discontinuation include the following criteria:

- Best medical interest of the subject at the discretion of the Investigator
- Initiation of alternative anticancer therapy (marketed or investigational)
- Withdrawal of consent for all follow-up
- Lost to follow-up
- Death

Subject disposition data will also be presented in data listings.

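### SAP 4.3 limits only the DLT half of the DLT analysis set to the dose evaluation phase, so as worded the set's size is wrong and depends on outcome

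*SAP*

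**What the plan says.** SAP 4.3 builds the set from two membership rules.

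- First rule: "All subjects in the dose escalation who experience a DLT at any time during the DLT Evaluation Period".
- Second rule: "All subjects with no DLT who receive at least 75% of the scheduled doses of durvalumab and tremelimumab", with further conditions on vaccinations received in the first two cycles, safety assessments and major protocol violations. It names no phase.

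Protocol 4.1.2 has the same two rules but puts a phase limit on neither. Its first rule begins "All subjects who experience a DLT at any time during the DLT Evaluation Period (as defined in Section 3.1.9". The protocol sets the scope through the use of the set instead: "In the dose evaluation phase, for the primary endpoint of determining DLTs and the RCD", the analysis is based on this population.

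SAP 2.2 says of the DLT endpoint: "This applies to Dose Evaluation subjects during the DLT Evaluation period". Protocol 3.1.7.1 likewise places DLT evaluation in the dose evaluation cohorts.

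The SAP's phrase for the phase is an old one. Protocol 8.1 records that Amendment 2 renamed dose escalation as dose evaluation, so I read the two as the same.

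**The concern.** A phase limit on one half of an analysis set makes membership depend on the outcome. Expansion subjects can satisfy the second rule, because its conditions are set by cycle and both phases use the same dosing schedule (Protocol 3.1.7). They can also have a recorded DLT. The evaluation window is defined by time on treatment ("DLTs will be observed over a period of the first 2 cycles of the combination therapy"), and Protocol 3.1.10 makes a DLT a reason for stopping treatment in any subject. Among expansion subjects, those without a DLT come in and those with one stay out.

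DLTs are a primary endpoint of the dose evaluation phase, and SAP 1.0 makes the SAP's tabulations the basis of the study report's results. SAP 5.0 adds that "the number of subjects in each population (ITT and PP) and subjects that were removed from a population will be summarized". At stake are a reported population size that misdescribes the evidence behind the RCD and, under one further condition, the denominator of the DLT rate.

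**Working it through.** **Inputs**

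- Per arm at the RCD: 6 dose evaluation subjects plus 14 expansion subjects, 6 + 14 = 20 (Protocol 3.1.7.2).
- RCD rule: at most 1 of 6 with a DLT (Protocol 3.1.7.1). An arm that expands therefore has x = 0 or 1 DLT among its 6.
- Number of expansion subjects with an in-window DLT, y: assumed, because the documents give no DLT rate.
- All DLT-free subjects are assumed to meet the exposure and assessment conditions.

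**Check on the plan's own figures.** The protocol's only computed safety figures are the Clopper-Pearson intervals at n = 20 in Section 3.1.6. They reproduce: 1/20 gives 0.00127 to 0.24873, and 2/20 gives 0.01235 to 0.31698.

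**Set size under SAP 4.3 as written**

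N = x (dose evaluation, DLT) + (6 − x) (dose evaluation, no DLT) + (14 − y) (expansion, no DLT) = 20 − y.

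The size under the scope in SAP 2.2 and Protocol 4.1.2 is 6, whatever y is.

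**Rate if that set were used alone as the denominator, x = 1**

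| y | SAP 4.3 as written, 1/(20 − y) | Dose evaluation only |
|---|---|---|
| 0 | 1/20 = 5.0% | 1/6 = 16.7% |
| 1 | 1/19 = 5.3% | 1/6 = 16.7% |
| 2 | 1/18 = 5.6% | 1/6 = 16.7% |
| 4 | 1/16 = 6.3% | 1/6 = 16.7% |

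The intended rate is 0.1667/0.050 = 3.3 times the literal one at y = 0, and 0.1667/0.0625 = 2.7 times at y = 4. For scale, the exact 95% interval is 0.4% to 64.1% for 1/6 and 0.1% to 27.3% for 1/18.

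With x = 0 the estimate is 0% either way. Only the apparent precision changes: the upper limit is 45.9% for 0/6, 16.8% for 0/20 and 20.6% for 0/16.

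**How often the outcome dependence would act.** The chance that at least one of 14 expansion subjects has an in-window DLT is 1 − (1 − p)^14. For assumed p of 10%, 20% and 30% it is 77%, 96% and 99%. The expected number left out, 14p, is 1.4, 2.8 and 4.2.

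**The case against.** The strongest reply is that the plan settles the scope elsewhere. SAP 2.2, Protocol 3.1.7.1 and Protocol 4.1.2 all say dose evaluation. Protocol 3.1.11 and SAP 11.1 tie DLT evaluability and replacement to that phase, and SAP 11.7 places DLT review in those cohorts. On this view the added phrase in SAP 4.3 is an incomplete clarification towards the protocol's scope, and a programmer who reads the whole SAP would get 6. That stands as evidence of intent. It does not amend the membership rule, and SAP 4.3 is the only place in the SAP that states it.

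Three stronger readings are tempting, and the documents do not support them.

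- *The primary DLT rate will be misreported.* SAP 4.3 assigns its set to no analysis, SAP 9.1.1 names no population for the DLT table, and SAP 4.1 uses the ITT population for safety analyses. The protocol does link the set to the DLT endpoint, but only within dose evaluation, which gives 1/6. The diluted rates need the 4.3 flag to be used without the SAP 2.2 limit.
- *Expansion DLTs disappear from the report.* They do not. SAP 9.1.1 lists DLTs and all adverse events, and SAP 5.0 has DLT as a reason for stopping treatment.
- *The right comparator is the rate in all 20 subjects.* At y = 4 that would be 5/20 = 25% against 6.3%, a striking contrast. But neither document plans a pooled DLT rate; the intended result is 1/6 for every y.

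**Conclusion.** The defect is real and limited. As worded, SAP 4.3 gives a set of 20 − y per arm at the RCD where 6 is intended, and for expansion subjects membership turns on the event being measured. That follows from the text, given 6 + 14 subjects who are otherwise evaluable. Where the size would appear is less certain: SAP 5.0 reports population counts but refers only to PP, without saying which of the two PP populations it means.

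The drop from 16.7% to between 5.0% and 6.3% is conditional. It rests on assumed counts (one DLT among the 6, up to four among the 14) and on the 4.3 flag serving alone as the denominator.

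A reader might also infer that the recommended dose is at risk. It is not: the RCD is set at the interim safety reviews under the 1-of-6 rule (Protocol 3.1.7.1 and 3.1.13), before the arm expands. The correction is still worth making, because the population for a primary endpoint should not have to be inferred against its own definition.

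**What to change.** Put both rules of SAP 4.3 under one lead-in that restricts the set to subjects in the dose evaluation phase who either (1) have a DLT within the DLT Evaluation Period or (2) have no DLT and meet the existing exposure, assessment and violation conditions, left unchanged. Use the current phase name.

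Add a sentence saying that this set is used for the primary DLT/RCD analysis, as Protocol 4.1.2 already provides.

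The cost is a few words in one SAP section and one line in the population-flag program. It needs no new data and leaves the 3 + 3 rule alone.
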